Incidence of treatment discontinuation due to lack of efficacy (up to Week 56/End of Treatment)	ITT	Logistic Regression	BL WOMAC Pain, BL Diary Average Pain, Index Joint (Knee/Hip), Highest KL grade (2, 3 or 4), NSAID cohort, Treatment Group	Observed	Secondary Endpoint Analysis

090017764931816561 Approved On: 08-10-2019 08:56 (GMT)

Incidence of rescue medication use during Weeks 2, 4, 8, 16, 24, 32, 40, 48, and 56	ITT	Logistic Regression	BL WOMAC Pain, BL Diary Average Pain, Index Joint (Knee/Hip), Highest KL grade (2, 3 or 4), NSAID cohort, Treatment Group	LOCF	Secondary Endpoint Analysis
Number of days of rescue medication use during Weeks 2, 4, 8, 16, 24, 32, 40, 48, and 56	ITT	Negative Binomial	BL WOMAC Pain, BL Diary Average Pain, Index Joint (Knee/Hip), Highest KL grade (2, 3 or 4), NSAID cohort, Treatment Group	LOCF	Secondary Endpoint Analysis
Amount (mg) of rescue medication taken during Weeks 2, 4, 8 and 16	ITT	Negative Binomial	BL WOMAC Pain, BL Diary Average Pain, Index Joint (Knee/Hip), Highest KL grade (2, 3 or 4), NSAID cohort, Treatment Group	LOCF	Secondary Endpoint Analysis
EQ-5D-5L dimensions (Mobility; Self-care; Usual activity; Pain/Discomfort; Anxiety/Depression) and Overall Health Utility at Baseline and Weeks 16, 24 and 56	ITT	Summary	NA	Observed	Secondary Endpoint Analysis
EQ-VAS at Baseline and Weeks 16, 24 and 56	ITT	Summary	NA	Observed	Secondary Endpoint Analysis
mPRTI endpoints (willingness to re-use; patient preference) at Weeks 16 and 56	ITT	CMH test	Treatment group [1]	Observed	Secondary Endpoint Analysis
TSQM endpoints (satisfaction with effectiveness, side effects and convenience, and overall satisfaction) at Weeks 16 and 56	ITT	ANCOVA	BL Diary Average Pain, Index Joint (Knee/Hip), Highest KL grade (2, 3 or 4), NSAID cohort, Treatment Group (Study site as a random effect)	Observed	Secondary Endpoint Analysis
WPAI endpoints (% work time missed; % impairment while working; % overall work impairment; % activity impairment) at Weeks 16, 24 and 56	ITT	ANCOVA	BL Score, BL Diary Average Pain, Index Joint (Knee/Hip), Highest KL grade (2, 3 or 4), NSAID cohort, Treatment Group (Study site as a random effect)	Observed	Secondary Endpoint Analysis
Healthcare Resource Utilization at baseline, weeks 56 and 64	ITT	Descriptive Summary	Treatment group	Observed	Secondary Endpoint Analysis

Change from Baseline in LEAS to Weeks 4, 8, 16, 24, and 56, and worst post-baseline score.	ITT	CMH test	Treatment group [1]	LOCF (weeks 4, 8, 16, 24, and 56) and worst score	Secondary Endpoint Analysis
Change from Baseline in Accelerometry endpoints (daily minutes of physical activity, MVPA and bouts MVPA; daily step count; daily physical activity counts) to Weeks 16 and 56	Accelerometry analysis set	negative binomial	BL Score, BL Diary Average Pain, Index Joint (Knee/Hip), Highest KL grade (2, 3 or 4), NSAID cohort, Treatment Group	Observed	Secondary Endpoint Analysis
Change from Baseline in Accelerometry endpoints (daily minutes of physical activity, MVPA and bouts MVPA; daily step count; daily physical activity counts) to Week 56	Accelerometry analysis set	negative binomial	BL Score, BL Diary Average Pain, Index Joint (Knee/Hip), Highest KL grade (2, 3 or 4), NSAID cohort, Treatment Group	LOCF	Secondary Endpoint Analysis
Incidence of primary composite adjudication joint safety endpoint	ITT	Poisson model for risk difference (exposure-adjusted)	Exposure, exposure*treatment	Observed	Primary Joint Safety Analyses
Incidence of primary composite adjudication joint safety endpoint	ITT	Poisson model for risk ratio (exposure-adjusted)	Treatment group, offset by log-exposure	Observed	Secondary Joint Safety Analyses
Incidence of primary composite adjudication joint safety endpoint	ITT	Exact analyses for risk difference and ratio (percentage)	Treatment group	Observed	Secondary Joint Safety Analyses
Incidence of secondary composite endpoint, individual adjudication joint safety endpoints (RPOA-1, RPOA-2, RPOA-1/2, SIF, Primary ON, Pathological fracture), TJR, and TJR and any adjudication outcome	ITT	Poisson model for risk difference (exposure-adjusted)	Exposure, exposure*treatment	Observed	Secondary Joint Safety Analyses
Incidence of secondary composite endpoint, individual adjudication joint safety endpoints (RPOA-1, RPOA-2, RPOA-1/2, SIF, Primary ON, Pathological fracture), TJR, and TJR and any adjudication outcome	ITT	Poisson model for risk ratio (exposure-adjusted)	Treatment group, offset by log-exposure	Observed	Secondary Joint Safety Analyses

090017764931816561Approved/Approved On: 08-10-2019 08:56 (GMT)

09/01/2019 17:56:56 Approved On: 08/10/2019 08:56 (GMT)

Incidence of secondary composite endpoint, individual adjudication joint safety endpoints (RPOA-1, RPOA-2, RPOA-1/2, SIF, Primary ON, Pathological fracture), TJR, and TJR and any adjudication outcome	ITT	Exact analyses for risk difference and ratio (percentage)	Treatment group	Observed	Secondary Joint Safety Analyses
Time to joint safety event (Primary Composite, Secondary Composite, Individual Adjudication Events, TJR, TJR and any adjudication outcome)	ITT	Log-Rank (with KM estimates)	Treatment Group	Observed	Secondary Joint Safety Analyses
Incidence of Bland-Altman defined progression of OA for subjects with OA of the Hip (KL2,3) at Weeks 56/ET and 80/ET, and Weeks 56 and 80 (based on window)	ITT	Logistic Regression	BL JSW, Treatment Group	Observed	Radiographic safety endpoint
Incidence of Bland-Altman defined progression of OA for subjects with OA of the Knee (KL2,3) at Weeks 56/ET and 80/ET, and Weeks 56 and 80 (based on window)	ITT	Logistic Regression	BL JSW, Treatment Group	Observed	Radiographic safety endpoint
Change from Baseline in JSW for subjects with OA of the Hip (KL 2, 3) at Weeks 56/ET and 80/ET, and Weeks 56 and 80 (based on window)	ITT	ANCOVA	BL JSW, Treatment Group (Study site as a random effect)	Observed	Radiographic safety endpoint
Change from Baseline in JSW for subjects with OA of the Knee (KL 2, 3) at Weeks 56/ET and 80/ET, and Weeks 56 and 80 (based on window)	ITT	ANCOVA	BL JSW, Treatment Group (Study site as a random effect)	Observed	Radiographic safety endpoint
Change from baseline to Weeks 2, 4, 8, 16, 24, 32, 40, 48, 56, 64 and 80 in the NIS score, and Change from Baseline to Worst post-Baseline NIS score	ITT	CMH test	Treatment Group [1]	LOCF (Weeks 2, 4, 8, 16, 24, 32, 40, 48, 56, 64, 80), Worst post-baseline score	Safety Analysis
Survey of Autonomic Symptoms (SAS), number of symptoms and total impact score (by visit and change from Baseline)	ITT	Summary	NA	Observed	Safety Analysis

[1] CMH test will be stratified by the levels of the combined stratification parameters (18 levels). If there are <15 subjects in any combined stratification level then the CMH test will be unstratified.

09001776e49378b656\Approved\Approved On: 08-10-2019 08:56 (GMT)

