Radiographs of each shoulder, knee and hip (and any other major joint imaged at Screening or identified as at risk [refer to Section 7.4.4] during the study) should be performed as soon as possible after the decision to withdraw from the study has been made, provided at least 30 days have passed since the last set of X-rays were collected. Subjects that were determined to have Kellgren-Lawrence Grade 3 or 4 osteoarthritis in any knee or hip joint at Screening should also have an MRI of each knee and hip performed. The remainder of efficacy and safety assessments should be done at the scheduled first visit which is to occur approximately 8 weeks after the last dose of SC investigational product (as described in Section 6.4.1.1). The site should also schedule the subject for two additional clinic visits. The second visit should be scheduled to occur approximately 16 weeks after the subject's last dose of SC investigational product (which corresponds to more than 5 times the elimination half-life of tanezumab) to collect safety and efficacy data (as described in Section 6.4.1.3). Once the clinic visit 16-weeks after the last administration of SC investigational product has been completed and final efficacy assessments have been collected, standard of care treatment will be offered to subjects for the remaining 8 weeks of the required Safety Follow-up period. Standard of care treatment may be initiated as needed and should be recorded on the concomitant medication Case Report Form (CRF). The third and final clinic visit should be scheduled to take place approximately 24-weeks after the subject received the last dose of SC investigational product. That visit (as described in Section 6.4.1.5), will include repeat radiographs of each shoulder, knee and hip (and any other major joint imaged at Screening or identified as at risk during the study) providing at least 30 days have elapsed since the last radiographs were obtained. Subjects that were determined to have Kellgren-Lawrence Grade 3 or 4 osteoarthritis in any knee or hip joint at Screening should also have an MRI of each knee and hip performed. Every effort should be made to have the subject agree to complete the entire 24-week Early Termination Safety Follow-up described above.

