# 7.2.7. Assessment of Health Care Resource Utilization

The utilization of health care resources (eg, doctor office visits, hospitalizations, surgeries or procedures, etc.) during the 3 months prior to Baseline will be assessed by questionnaire at Baseline (Day 1). In addition, Health Care Resource Utilization will be collected at study visits at Weeks 64 and 80 (or at early termination, as described in Section 6.4). Subjects will record their responses using IRT.

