- *Work Productivity and Activity Impairment Questionnaire for Osteoarthritis (WPAI:OA) impairment scores change from Baseline to Weeks 16, 24, 56 and 64.*
- *EuroQol 5 Dimension (EQ-5D-5L™) dimensions and overall health utility score at Baseline and Weeks 8, 16, 24, 40, 56 and 64.*
- *Treatment Satisfaction Questionnaire Medicine v.II (TSQM v.II) satisfaction with effectiveness, side effects and convenience, and overall satisfaction at Weeks 16 and 56.*
- *Patient Reported Treatment Impact Assessment-Modified (mPRTI) at Weeks 16 and 56.*
- *Incidence and Time to discontinuation due to Lack of Efficacy.*
- *Usage of rescue medication (incidence and number of days of use) during Weeks 2, 4, 8, 16, 24, 32, 40, 48, 56 and Week 64.*
- *Usage of rescue medication (amount taken) during Weeks 2, 4, 8 and Week 16.*
- *Health Care Resource Utilization at Baseline and Weeks 64, and 80.*

Note, in this document where reference is made to three co-primary efficacy endpoints this relates to all countries except Japan, where there are only two co-primary efficacy endpoints (WOMAC Pain and Physical Function subscale scores).

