The Baseline and Weeks 8, 16, 24, 40, 56 and 64 responses in the five dimensions (mobility; self-care; usual activities; pain/discomfort; anxiety/depression) and overall health utility score from the EuroQol 5 Dimensions 5 Level (EQ-5D-5L) will be summarized by treatment group. This summary will use observed data only (no imputation for missing data). The calculation of the overall health utility score is described in [Appendix 1.4](#).

An additional question, called the EQ-VAS asks the subject to rate their health today using a VAS scale from 0 (the worst health you can imagine) to 100 (the best health you can imagine). This will be summarized along with the health utility score. A table showing number and percentage of subjects will summarize the response for each dimension (item) of the EQ-5D at each time point. These summary tables will be shown by treatment group. In addition, for each treatment and each time point assessed, descriptive statistics (mean, standard deviation, median, number of subjects) will be shown for the health utility score, and the EQ-VAS measure of health today.

7. Work Productivity and Activity Impairment Questionnaire for Osteoarthritis (WPAI:OA).

The change from Baseline to Weeks 16, 24, 56 and 64 in the 4 impairment scores of the Work Productivity and Activity Impairment Questionnaire for Osteoarthritis (WPAI:OA) will be summarized by treatment group.

This summary will use observed data only (no imputation for missing data). The calculation of these endpoints is described in [Appendix 1.4](#).

The summary will show number and percentage of subjects with a decrease, no change, and an increase in score for the change from Baseline to each time point, as well as descriptive statistics (mean, standard deviation, median, number of subjects) of the Baseline and change at Weeks 16, 24, 56, and 64.

Change from baseline at Weeks 16, 24, and 56 in the 4 parameters will be analyzed using the ANCOVA model described above for the primary endpoint using covariates of the corresponding Baseline score, Baseline diary average pain, Index Joint, Highest KL grade (2, 3 or 4), NSAID cohort and Treatment, with Study Site as a random variable.

8. Health Care Resource Utilization.

The Health Care Resource Utilization data at Baseline, Weeks 64 and 80 will be summarized.

09001776e193781b6561Approved\Approved On: 08-10-2019 08:56 (GMT)

9. Treatment Satisfaction Questionnaire Medicine v.II (TSQM v.II).

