10. APPENDICES

Appendix 1. DATA DERIVATION DETAILS

Appendix 1.1. Definition and Use of Visit Windows in Reporting

Study visits are planned at Screening, Baseline and then at post-baseline Weeks 2, 4, 8, 16, 24, 32, 40, 48, 56, 64 and 80. If a subject discontinues from the trial then there will be an Early Termination Follow-Up period and for those who refuse, ideally, an Early termination visit. To account for this visit and any early or late scheduled visits (compared to the target study days) we define ‘windows’ to be able to allocate each efficacy observation to a single specific study visit. For the assessments made at each planned study visit (eg, WOMAC subscales, Patient Global Assessment of Osteoarthritis etc.) these visit windows are shown below. When multiple observations occur in a visit window, the observation closest to the protocol specified target day will be used, noting that the latter will be used in the case of a tie.

Visit	Target Study Day	Window
Screening [1]	Variable (up to 37 days prior to baseline visit)	[No lower limit, Day -8]
Baseline	1 (defined as initial day of study drug administration)	[-7,1]
Week 2	15	[2,22]
Week 4	29	[23,43]
Week 8	57	[44,85]
Week 16	113	[86,141]
Week 24	169	[142,197]
Week 32	225	[198, 253]
Week 40	281	[254, 309]
Week 48	337	[310, 365]
Week 56	393	[366, 421]
Week 64	449	[422, 477]

[1] Only efficacy data collected at screening is WOMAC Pain subscale.

One additional window will be created relative to the date of last SC dose for summaries of efficacy data collected beyond the planned treatment period. This window will include data from 16 +/- 4 weeks past the date of the last SC dose. The target day is 113 days after the last SC dose, with a window of [85, 141] days after the last SC dose. If multiple observations occur in this visit window, the observation closest to the specified target day will be used, noting that the latter will be used in the case of a tie.

For the assessments not made at each planned study visit, broader visit windows are shown below. When multiple observations occur in a visit window, the observation closest to the protocol specified target day will be used, noting that the latter will be used in the case of a tie.

LEAS

Visit	Target Study Day	Window
Baseline	1 (defined as initial day of study drug administration)	[-7,1]
Week 4	29	[2,43]
Week 8	57	[44,85]
Week 16	113	[86,141]
Week 24	169	[142,281]
Week 56	393	[282, 477]
Week 80/End of Study	561	[478, no upper limit]

EQ-5D-5L

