5	How dissatisfied are you by side effects that interfere with your mental function (eg, ability to think clearly, stay awake)?	1 (Extremely dissatisfied) to 5 (Not at all dissatisfied)
6	How dissatisfied are you by side effects that interfere with your mood or emotions and ability to function (eg, anxiety/fear, sadness, irritation/anger)?	1 (Extremely dissatisfied) to 5 (Not at all dissatisfied)
7	How satisfied or dissatisfied are you with how easy the medication is to use?	1 (Extremely dissatisfied) to 7 (Extremely satisfied)
8	How satisfied or dissatisfied are you with how easy it is to plan when you will use the medication each time?	1 (Extremely dissatisfied) to 7 (Extremely satisfied)
9	How satisfied or dissatisfied are you by how often you are expected to use/take the medication?	1 (Extremely dissatisfied) to 7 (Extremely satisfied)
10	How satisfied are you that the good things about this medication outweigh the bad things?	1 (Extremely dissatisfied) to 7 (Extremely satisfied)
11	Taking all things into account, how satisfied or dissatisfied are you with this medication?	1 (Extremely dissatisfied) to 7 (Extremely satisfied)

The scoring of the 4 satisfaction parameters are shown in the table below.

TSQM Parameter	Scoring
Effectiveness	$[(\text{Item 1} + \text{Item 2}) - 2] / 12 * 100$
Side Effects	$[(\text{Item 4} + \text{Item 5} + \text{Item 6}) - 3] / 12 * 100$ If one item is missing then: $[(\text{Sum of two completed items}) - 2] / 8 * 100$
Convenience	$[(\text{Item 7} + \text{Item 8} + \text{Item 9}) - 3] / 18 * 100$ If one item is missing then: $[(\text{Sum of two completed items}) - 2] / 12 * 100$
Global Satisfaction	$[(\text{Item 10} + \text{Item 11}) - 2] / 12 * 100$

The four parameters have a scale of 0-100, with 100 being the best (most satisfied) score.

0900177 (e-s) 1811656 Approved Approved On: 03-10-2019 08:56 (GMT)

Healthcare Resource Utilization (example using 3 month recall—8 week recall is also used in study)

Question	Response	Scoring
During the last 3 months, what services did you receive directly related to your osteoarthritis? 
 • Primary Care Physician • Neurologist • Rheumatologist • Physician Assistant or Nurse Practitioner • Pain Specialist • Orthopedist • Physical Therapist • Chiropractor • Alternative Medicine or Therapy • Podiatrist • Nutritionist/Dietician • Radiologist • Home healthcare services • Other 	Number of Visits	Response not selected = 0 Number of visits = 1-999

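### SAP 8.2.5 plans a Week 56 summary of health care resource utilization that is never collected, and the Week 64 window takes the later early-termination visit after any last dose up to Week 40

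*SAP*

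**What the plan says.** **Time points.** The HCRU row of SAP 8.2.5 reads "Healthcare Resource Utilization at baseline, weeks 56 and 64", with a descriptive summary of observed data. SAP 6.1 lists the endpoint as "Health Care Resource Utilization at Baseline and Weeks 64, and 80". SAP 8.2.2, item 8, states "The Health Care Resource Utilization data at Baseline, Weeks 64 and 80 will be summarized". Protocol 7.2.7 provides for a Baseline questionnaire and then says "Health Care Resource Utilization will be collected at study visits at Weeks 64 and 80", or at early termination. The protocol's Schedule of Activities marks Baseline, Week 64 and Week 80. The Week 56 procedure list (Protocol 6.2.16) has no HCRU.

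**Early terminators.** HCRU is completed at Early Termination Visit 2, 16 weeks after the last SC dose (Protocol 6.4.1.3), and at Visit 3, 24 weeks after it (Protocol 6.4.1.5). Once the 16-week visit is done, Protocol Section 3 says that "standard of care treatment will be offered to subjects for the remaining 8 weeks of the required Safety Follow-up period". Subjects who complete treatment may start standard of care only after the Week 64 assessments, which also fall 16 weeks after the last SC dose.

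**Windows.** SAP Appendix 1.1 gives HCRU two post-baseline windows: Week 64 (target Day 449, Days 2 to 505) and Week 80 (target Day 561, from Day 506 with no upper limit). If several records fall in one window, "the observation closest to the protocol specified target day will be used", with the later one taken in a tie.

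**The concern.** The 8.2.5 row names a visit with no HCRU data and drops one that has data. A programmer working from the table would not produce the summary that the SAP text defines.

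The window matters more for the content of the summary. Early Termination Visit 2 is the natural counterpart of Week 64: both come 16 weeks after the last SC dose and before standard of care is allowed. Visit 3 is the counterpart of Week 80. Both early-termination records fall within Days 2 to 505 when the subject stopped well before Week 48, so the nearest-to-Day-449 rule has to choose between them. It favours the later one. Standard of care includes clinic-administered treatments such as joint injections, so its availability bears directly on what an HCRU questionnaire records.

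**Working it through.** **The SAP's own windows.** Target day = 7 × week + 1. Week 64: 7 × 64 + 1 = 449. Week 80: 7 × 80 + 1 = 561. The boundary is the midpoint, (449 + 561)/2 = 505. All three agree with Appendix 1.1.

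**Inputs for the selection.** SC doses are given at Baseline and Weeks 8, 16, 24, 32, 40 and 48. For a last dose on Day d, Visit 2 falls on d + 112 and Visit 3 on d + 168. The distance from Day 449 is shown in brackets.

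| Last SC dose | d | Visit 2 | Visit 3 | Taken as Week 64 |
|---|---|---|---|---|
| Baseline | 1 | 113 (336) | 169 (280) | Visit 3 |
| Week 8 | 57 | 169 (280) | 225 (224) | Visit 3 |
| Week 16 | 113 | 225 (224) | 281 (168) | Visit 3 |
| Week 24 | 169 | 281 (168) | 337 (112) | Visit 3 |
| Week 32 | 225 | 337 (112) | 393 (56) | Visit 3 |
| Week 40 | 281 | 393 (56) | 449 (0) | Visit 3 |
| Week 48 | 337 | 449 (0) | 505 (56) | Visit 2 |

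**Break-even.** The two distances are equal when the midpoint of the visits, d + 140, is 449, so d = 309. The tie goes to the later record. A Week 40 dose (Day 281) is 309 − 281 = 28 days short of that point. With assumed shifts of up to 7 days either way on the dose and on each visit, the selection did not change for any last dose.

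**Week 80 window.** Visit 3 reaches Day 506 only if d + 168 ≥ 506, that is, d ≥ 338. The last scheduled dose is on Day 337, so at nominal timing no early-termination record enters the Week 80 window. A Visit 3 one day late after a Week 48 dose does enter.

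**An example.** A subject stopped by the Week 16 response rule will normally have had the last dose at Week 8. That subject's Week 64 entry is the Day 225 record (Week 32, since 7 × 32 + 1 = 225), taken 8 weeks after standard of care became available. The Day 169 record, from before that point, is discarded.

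**No other rule removes these records.** SAP Section 8 excludes off-treatment data only from treatment-period summaries, up to Week 56. It says that all available data in the Week 64 window are used.

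**The case against.** Section 8.2.5 is only a summary table. The endpoint list, the analysis text and the windows all agree on Weeks 64 and 80, and with no Week 56 HCRU window no Week 56 column could be produced. That is right, so this part is a wording slip, but it still needs correcting. HCRU is also untested, outside the gatekeeping strategy, and cannot affect any primary or key secondary result. That stands too and limits the weight of the point.

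Appendix 1.1 adds one window anchored 16 weeks after the last SC dose, for efficacy data beyond the planned treatment period. It would capture Visit 2. However, it is set out with the assessments made at every visit, HCRU has its own table without it, and it would not change what the Week 64 window selects.

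A reader might infer several stronger things that the documents do not support:

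- **That the endpoint fails because treatment weeks are not measured.** The endpoint is defined at Weeks 64 and 80, and no study objective concerns resource use during treatment. The SAP says that "8 week recall is also used in study" without saying at which visit. From Day 449, an 8-week recall reaches back to Day 393 (449 − 56), the end of treatment. A 3-month recall, taken as 91 days, reaches Day 358, which is 5 weeks earlier. This is a design choice, not an error.
- **That all early terminators are affected.** Subjects who refuse follow-up have one combined visit (Protocol 6.4), and those with immediate joint replacement have one discontinuation visit (Protocol 6.4.2). Some will miss Visit 3, and a Week 48 last dose selects Visit 2.
- **That the Week 80 column holds completers only.** A late Visit 3 after a Week 48 dose enters it.
- **That the affected share is known, or known to differ by arm.** The documents give no discontinuation rates from which to compute either.
- **That the later records reflect standard of care in use.** It is permitted from Visit 2 and may not have been started.

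**Conclusion.** Two defects hold as written. The 8.2.5 row contradicts SAP 6.1, SAP 8.2.2, the HCRU windows and Protocol 7.2.7, both by naming Week 56 and by omitting Week 80. The Week 64 rule selects Early Termination Visit 3 over Visit 2 for last doses from Baseline to Week 40, six of the seven dosing visits. The Week 64 summary therefore combines completers seen before standard of care is permitted with early terminators seen after it is permitted.

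The second result assumes nominal timing and attendance at both visits. It is unchanged by 7-day shifts. The six-of-seven count refers to dosing visits, not to a proportion of subjects, which cannot be computed. The effect is confined to a descriptive secondary endpoint.

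**What to change.** Three edits to the SAP:

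1. Change the HCRU row in 8.2.5 to Baseline, Week 64 and Week 80.
2. In Appendix 1.1, assign HCRU by planned visit: Early Termination Visit 2 to Week 64 and Visit 3 to Week 80. State where a single combined early-termination record goes, since the planned-visit rule alone does not settle that. SAP 8.2.3.1 already takes this approach for radiographs, where Visit 3 counts with Week 80 whatever the study day.
3. Label both columns as post-treatment summaries, 16 and 24 weeks after the last SC dose for early terminators. For completers, who receive the last SC dose at Week 48, Week 64 is 16 weeks after it and Week 80 is 32 weeks after it but 24 weeks after the end of treatment. The label should say so.

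The cost is wording and a small programming change, made before unblinding. The records are already collected, so no new questionnaire, visit or protocol amendment is needed.
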